5.1.4.4 Vital Signs and Physical Exam

Vital signs will be presented in a data listing for the Safety Population.

[figure not shown]
Physical measurements taken at screening (height and weight) will be summarized by descriptive statistics.

[figure not shown]
Table 5-22 Physical Examination Analyses

Endpoint	Description	Timing	Methodology
Physical measurement	Summary of height, weight, and BMI	Screening	Continuous descriptives

5.1.4.5 Pregnancy Test Analyses

[figure not shown]
Urine pregnancy tests are taken at screening, treatment, and Month 3 exit visits. Subjects with a positive result will be summarized in a data listing.

[figure not shown]

5.1.6 Interim Analyses

No interim analysis is planned.

5.3 Changes in the Conduct of the Study or Planned Analyses

The PP definition in the study protocol was enhanced (see Table 5-1) to specifically exclude subjects who did not receive each assigned treatment on its assigned side for this paired-comparison study. The intent is that such cases would be identified as significant protocol deviations, but, in case they are not, the enhanced definition specifically excludes them from the PP population. Also, the study populations defined in the protocol were expanded (see Table 5-1) to include the screened population and the ITT population, because those definitions are needed for some of the data listings.

6. Data Handling and Analysis Conventions

6.1 Study Treatment Conventions

6.1.1 Analysis Days

Treatment Day for effectiveness, ISR, and AE are defined as follows:

Table 6-1 Analysis Day Definitions

Term	Description
Treatment Day	Relative to the treatment date
	• Day = analysis date – treatment date + 1
	 Day 1 = treatment date
Safety Day (including	Relative to the treatment date
AE and ISR)	
	• Day = analysis date – treatment date + 1
	 Day 1 = treatment date

6.2 Analysis Visit Windows

All scheduled and unscheduled visits with complete dates will be assigned visit windows and used for analysis. However, if a scheduled visit with incomplete date is available with no other visits with complete date during the visit window, then the visit with incomplete date may be used for analysis.

If there are multiple visits occurring within a single visit window with relevant data, the visit closest to the target day will be used in the analysis of the corresponding visit windows. If 2 visits are equal distance to the target day and are the same type of visit, then the later visit will be used.

If a subject's visit falls into the analysis window for a visit other than its nominal visit, but is not selected by the above decision rules, and if the subject had no other visits to represent its nominal visit, then that visit will used for analysis of its nominal visit (eg, a month 1 visit that falls into the month 3 window will instead be used for month 1 analysis if the subject has another visit that is selected for month 3 analysis).

Analysis visit windows for effectiveness endpoints and safety are defined as follows:

6.2.1 Effectiveness

The analysis visit windows for effectiveness endpoints are defined as follows. If treatment does not occur on the same day as randomization, the treatment date will be the reference date for post-treatment analysis.

Table 6-2 Effectiveness Analysis Visit Definitions

A 1 1 171 14 (TD 1 1)	TD 4 D 641 371 14	XX7* 1
Analysis Visit (Derived)	Target Day of the Visit	Window

Analysis Visit (Derived)	Target Day of the Visit	Window	
Screening	-30	< randomization	
Day 1	Day 1	Randomization to Treatment Day	
Month 1	Day 31	Treatment Day [2, 61]	
		post-treatment	
Month 3	Day 91	Treatment Day [62, 121]	
		post-treatment	
> Month 3	Not analyzed	Treatment Day > 121 post-	
		treatment	

6.2.2 Safety

Analysis visit windows do not apply to TEAEs and ISRs; they are by definition post-treatment.

6.3 Missing/Incomplete Date Conventions

In general, there will be no substitution of missing time or date. However, any partial information will be utilized to its full extent wherever sensible. For example, a medication may be classified as a prior medication if the partial information of the medication ending date with only month and year permits a determination that the medication ended prior to the treatment date of study treatment.

Partial dates occurring when calculation of study day is germane to the study outcome will be handled as follows, but only for purposes of summary tables; data will be displayed in the data listings as recorded:

If the year is missing, then the date will be treated as missing.

In general, if either the month or the day is missing, then the closest date to study treatment will be used. That is, an event occurring the year before treatment will use December and/or the last day of the month. An event occurring the year after treatment will use January and/or the first day of the month. Following are rules specific to AEs and concomitant medications.

All AEs with missing onset dates will be identified and the missing dates will be imputed as follows for analysis.

(1) For AE onset date: If day and month are missing, but year is available (../../yy), then the imputed day and month will be 01/01/yy. However, if the treatment date is during the same year, the onset date will instead be set to the treatment date. If the day is missing but the month and year are available (mm/../yy), then the imputed day will be mm/01/yy. However, if the treatment

date is during the same month and year, the onset date will instead be set to the treatment date. If an imputed date is prior to the screening visit, it will be reset to the screening date.

- (2) For AE stop dates: If day and month are missing, but year is available (../../yy), then the imputed day and month will be 12/31/yy. However, if the exit date is during the same year, the stop date will instead be set to the study exit date. If day is missing, but the month and year are available (mm/../yy), then the imputed day will be the last day of the month mm in the year yy. However, if the study exit date is during the same month and year, the stop date will instead be set to the study exit date.
- (3) If the AE onset month, day, and year are missing (../../..), then the treatment date will be used as the AE onset date. If the treatment date is missing, the randomization date will be used instead. If the randomization date is also missing, the screening date will be used instead.
- (4) If the AE has stopped, but the stop month, day, and year are missing (../../..), then the exit date will be used as the AE stop date. If the AE is indicated to be ongoing, the stop date will remain missing.

Concomitant medication and prior medication will be calculated using the following decision rules: (1) if the stop date of taking medication is prior to the treatment date, then it will be counted as prior medication; (2) if the start date of taking medication is on or after the treatment date, then it will be counted as concomitant medication; (3) if the start date of taking medication is prior to the treatment date and the stop date is on or after the treatment date, then it will be counted as both prior medication and concomitant medication; (4) if still unresolved, it will be counted as a concomitant medication.

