8.3.4 Safety Analyses

ISRs, procedural pain assessment, and AEs will be summarized using descriptive statistics. The primary safety analysis of ISRs and AEs will be summarized by the percentage (and 95% CI) of subjects who have the ISR (or AE) on both sides, by the percentage (and 95% CI) of subjects who have the ISR (or AE) on the cannula side and not on the needle side, and by the percentage (and 95% CI) of subjects who have the ISR (or AE) on the needle side and not on the cannula side. Also, the within-treatment percentage (and 95% CI) of subjects who have the ISR (or AE) will be summarized for the cannula side and, separately, for the needle side.

ISRs reported by subjects will be summarized by symptom, maximum reported severity, maximum reported duration (ie, calendar days from first occurrence to last reported occurrence during the 30-day ISR period), and number of ISR days (ie, calendar days with non-zero severity, after accounting for days with missing reports during the ISR duration). Adverse events will be summarized by System Organ Class and Preferred Term, and will be tabulated by duration, severity, causality, action taken, relationship to treatment, and outcome. The summary will include incidence rate as well as total number of events. AEs that occur before treatment will be listed, but not summarized.

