11.2 Timelines for Reporting

The TI (or designee) is to adhere to the following schedule in reporting different types of AEs.

Adverse Event Type	Reporting to Allergan	Start of Collection	End of Collection
AEs, ADEs	Record on AE eCRF upon awareness for review by the Clinical Monitor	Signing ICF	Last subject visit
SAEs, SADEs	Record on SAE Form and fax/email to Allergan within 24 hours of awareness	Signing ICF	Last subject visit

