5.1.4.2 Adverse Events

The following AE terms are defined:

Table 5-19 AE Terms

Term	Description
Treatment-	An AE that initially occurs or increases in severity on or after the treatment start date.
emergent AE	
(TEAE)	
Treatment-	A TEAE that is related to study treatment in the judgment of the investigator.
related TEAE	
(TR-TEAE)	

AEs, encompassing abnormalities and surgeries reported as occurring after the Screening Visit, will be coded using MedDRA version 20.0 or newer. A listing of all TEAEs will be presented. Also, unique subjects reporting AEs as well as number of events in the following AE categories will be summarized by treatment group and in total for the Safety Population as follows (ie, AEs at cheeks, AEs not at cheeks and all AEs combined). The overall summary tables of AE categories and the summary tables for TEAEs and TR-TEAEs that are grouped by SOC, PT and severity will be included within a CSR-appendix set of tables. The other AE summary tables listed will be generated within a supplemental set of tables.

Table 5-20 AE Summaries

Endpoint	Description	Timing	Methodology
Overall summary	Overall summary only for the following categories:	Treatment	Categorical counts
	 Treatment-emergent AEs (TEAEs) Treatment-related TEAEs All Serious AEs (SAE) 		
	Treatment-related SAE		
	Discontinued due to TEAEDeaths		
TEAEs	 by SOC and PT by SOC, PT, and severity (mild, moderate, severe) by SOC, PT, and duration (≤ 7 days, 8-14 days, 15-30 days, > 30 days) non-serious and occur ≥ 5%, by SOC and PT 	Treatment	Categorical counts
TR-TEAEs	by SOC and PTby SOC, PT, and severity	Treatment	Categorical counts
SAEs ¹	Overall summary and by PT	Treatment	Listing
AEs leading to discontinuation ¹	Overall summary and by PT	Treatment	Listing

¹ Subjects who report ≥ 1 AE in the AE category and all AEs for those subjects will be listed. SOCs will be sorted alphabetically; PTs will be sorted in descending frequency across treatments (cannula and needle).

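### The AE onset-date rules in SAP 6.3 never check the stop date, so an event that ended before treatment can be counted as treatment-emergent

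*SAP*

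**What the plan says.** SAP 6.3 gives numbered rules for incomplete AE dates. Three branches lead to the treatment date as onset:

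- Rule (1), only the year known: "However, if the treatment date is during the same year, the onset date will instead be set to the treatment date".
- Rule (1), month and year known: if the treatment "date is during the same month and year, the onset date will instead be set to the treatment date".
- Rule (3), nothing known: "then the treatment date will be used as the AE onset date".

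The only bound stated for an imputed onset is a lower one, in rule (1): "If an imputed date is prior to the screening visit, it will be reset to the screening date". There is no upper bound at the stop date.

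TEAE status depends on timing against treatment. SAP Table 5-19 defines a TEAE as "An AE that initially occurs or increases in severity on or after the treatment start date". Table 5-20 then tabulates TEAEs "by SOC, PT, and duration (≤ 7 days, 8-14 days, 15-30 days, > 30 days").

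Protocol 8.3.4 treats earlier events differently: "AEs that occur before treatment will be listed, but not summarized". Protocol 11.1.1 and 11.2 start AE collection at consent, so such events will be in the database if they occur.

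**The concern.** Using the treatment date for an unknown onset is a sound conservative convention when nothing shows whether the event began before or after the injection. It stops being conservative when the record shows that the event was over before the injection. In that case the rule replaces a known ordering with an impossible one.

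Two things are at stake. An event that Protocol 8.3.4 confines to listings would enter the TEAE summaries, and SAP 5.3 does not list this as a change from the protocol. The imputed onset would also fall after the stop, which leaves no meaningful duration for the planned duration table. Because SAP 6.3 imputes dates for summary tables only and lists them as recorded, the listing of TEAEs could show an event with a recorded stop date before treatment.

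**Working it through.** The plan gives no figure to reproduce. The check is to apply the rules as written to constructed dates.

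**Inputs**

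- Onset rules (1) and (3), stop rule (2) and the reset to screening: SAP 6.3.
- TEAE if the imputed onset is on or after the treatment date: SAP Table 5-19.
- Assumed dates: screening 18 Feb 2018, treatment 20 Mar 2018. The 30-day gap follows the Day -30 screening target in SAP Tables 5-14 and 6-2. The actual window in Table 6-2 is any time before randomization.
- Duration: no AE formula is stated, so both stop − onset and stop − onset + 1 are shown.
- Planned number treated: 60 (Protocol 5.1).

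**Results under the current rules**

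| Recorded onset | Stop date used | Imputed onset | TEAE | Stop − onset | With + 1 |
|---|---|---|---|---|---|
| Mar 2018, day missing | 10 Mar | 20 Mar | yes | −10 | −9 |
| 2018 only | 25 Feb | 20 Mar | yes | −23 | −22 |
| Wholly missing | 25 Feb | 20 Mar | yes | −23 | −22 |
| 2018 only | Feb 2018, day missing, so 28 Feb | 20 Mar | yes | −20 | −19 |
| Mar 2018, day missing | 19 Mar | 20 Mar | yes | −1 | 0 |
| Feb 2018, day missing | 25 Feb | 1 Feb, reset to 18 Feb | no | 7 | 8 |
| Mar 2018, day missing | 25 Mar | 20 Mar | yes | 5 | 6 |
| Mar 2018, day missing | Mar 2018, day missing, so 31 Mar | 20 Mar | yes | 11 | 12 |

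The first five rows are the fault: the event ended before 20 Mar, yet it is classed as treatment-emergent. The last three rows mark its limits. An onset known to lie in an earlier month is not moved to the treatment date. A stop on or after treatment causes no conflict. A partial stop in the treatment month is imputed to the end of the month (or to the exit date, if exit falls in that month), so it causes none either.

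**Size per subject.** 1/60 = 0.0167, or about 1.7 percentage points. This is a ceiling: it applies only if the subject has no other event in that row of the table.

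**Comparison within the same section.** The medication rules in SAP 6.3 test the stop date first and class a medication that ended before treatment as prior. The AE rules have no matching step.

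**The case against.** The best defence is that the text already points to the right answer. SAP 6.3 opens with a general principle that partial information should be used as fully as is sensible, and its example uses an end date to show that something finished before treatment. An onset after a recorded stop is not sensible. Such an event also does not meet the TEAE definition in substance, and Protocol 8.3.4 excludes it from the summaries. A careful programmer might therefore override the rule.

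That has weight, but it does not close the gap. The example concerns a medication. The AE rules follow as specific rules in mandatory terms, and the general principle does not clearly override them. The result would depend on who writes the program. The separate specification mentioned in SAP 6.4 is about how imputed values appear in listings, not how onset is derived.

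The objection on frequency stands. The fault needs a pre-treatment AE, an onset incomplete in one of the three ways, and a stop date (recorded or imputed) before treatment. Protocol 11.2 tells sites to "Record on AE eCRF upon awareness for review by the Clinical Monitor", Protocol 11.1.1 has AEs queried at each visit after screening, and Protocol 7.5 provides for source verification. A site that knows the end of an event but not its start should be uncommon.

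A reader might go further and infer that the TEAE rates or the duration table will be materially distorted. The documents do not support that. They give no count of such events and no AE duration formula, and they do not say how an impossible duration would be tabulated. The lowest duration class has no stated lower limit, so a negative value could land there, but that is a possibility and not a stated rule.

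**Conclusion.** The point holds as a narrow fault in a stated rule. Read literally, rules (1) and (3) of SAP 6.3 can turn an AE that ended before treatment into a TEAE with an onset after its stop, contrary to Protocol 8.3.4.

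The effect is minor. How many events will qualify cannot be derived from the documents, and the number may be zero. The ceiling of 1.7 percentage points per affected subject assumes that the planned 60 are treated. Only the AE summary tables are involved; the primary effectiveness analysis and the diary-based injection site responses do not use these rules. The case rests on the AE rules being applied as written, without a programmer invoking the general principle.

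**What to change.** Add one condition to rules (1) and (3) of SAP 6.3, for example:

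*Where the complete or partial stop date of an AE shows that it ended before the treatment date, the treatment date is not used as onset. The onset is the later of the screening date and the first day of the known onset month or year (the screening date if the onset is wholly missing), and is never later than the stop date. The AE is classed as pre-treatment.*

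The condition must be that the stop falls before treatment, not merely that a stop date is known; otherwise genuine TEAEs with a recorded end would drop out of the tables. All other AEs, including those with a known stop on or after treatment, keep the current conservative rule.

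With this condition, the five problem rows become pre-treatment events. Their onsets, in table order, are 1 Mar, 18 Feb, 18 Feb, 18 Feb and 1 Mar, and stop − onset is 9, 7, 7, 10 and 18 days (one more with + 1). The last three rows do not change.

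Stating the AE duration formula in SAP 5.1.4.2 would remove the remaining ambiguity. The cost is a sentence or two in the SAP and one programming check, made before database lock, with no new data.

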6.4 Imputed Value Listing Conventions

In general, listings will present the actual partial or missing values rather than the imputed values that may be used in endpoint derivation. In instances where imputed values will be presented, imputed values will be flagged. Actual rules will be fully defined in the table, figure, and data listing specification document.

7. References

- 1. Newcombe, RG. "Improved confidence intervals for the difference between binomial proportions based on paired data", Statistics in Medicine, 17, 2635-2650 (1998).
- 2. May, WL and Johnson, WD. "The validity and power of tests for equality of two correlated proportions", Statistics in Medicine, 16, 2127-2136 (1997).
- 3. Fleiss, JL. Statistical Methods for Rates and Proportions, 2nd edn, Wiley, New York, 1981.

ALLERGAN

Statistical Analysis Plan 1650-801-008

Date (DD/MMM/YYYY)/Time (PT)	Signed by:	Justification
